6.2. Exclusion Criteria

Patients will be excluded from study enrollment if they meet any of the following criteria at screening:

Medical Conditions

- [14] Have any other condition (including known drug or alcohol abuse, or psychiatric disorder including eating disorder) that precludes the patient from following and completing the protocol
- [15] Have hypoglycemia unawareness, as judged by the investigator
- [16] Have had more than 1 episode of severe hypoglycemia (defined as requiring assistance due to neurologically disabling hypoglycemia) within the last 6 months prior to screening
- [17] Have had more than 1 emergency room visit or hospitalization due to poor glucose control (hyperglycemia or diabetic ketoacidosis) within 6 months prior to screening (Visit 1)
- [18] Have clinically significant cardiovascular disease within the last 6 months prior to screening, defined as stroke, decompensated heart failure New York Heart Association class III or IV (Appendix 6), myocardial infarction, unstable angina pectoris, or coronary arterial bypass graft

[19] Renal:

- History of renal transplantation
- o Currently receiving renal dialysis
- o Serum creatinine >2.0 mg/dL (177 μmol/L) at screening
- [20] Hepatic: Have obvious clinical signs or symptoms of liver disease (for example, acute or chronic hepatitis, or cirrhosis) or elevated liver enzyme measurements as indicated below at screening (Visit 1):
 - Total bilirubin level (TBL) \ge 2X the upper limit of normal (ULN) (with the exception of Gilbert's syndrome) as defined by the central laboratory,

OR

 Alanine aminotransferase (ALT) ≥3X ULN as defined by the central laboratory

OR

- Aspartate aminotransferase (AST) ≥3X ULN as defined by the central laboratory
- [21] Malignancy: Have active or untreated malignancy, have been in remission from clinically significant malignancy (other than basal cell or squamous cell skin cancer) for less than 5 years, or are at an increased risk for developing cancer or a recurrence of cancer, in the opinion of the investigator
- [22] Have any hypersensitivity or allergy to any of the insulins or excipients used in this trial
- [23] Have hypersensitivity or allergy to any of the ingredients in the standardized test meal (MMTT) (for example, nut allergy)

- [24] Hematologic: Have had a blood transfusion or severe blood loss within 90 days prior to screening or have known hemoglobinopathy, hemolytic anemia, or any other traits of hemoglobin abnormalities known to interfere with measurement of HbA1c
- [25] Have presence of clinically significant gastrointestinal disease (for example, clinically active gastroparesis associated with wide glucose fluctuations), in the opinion of the investigator
- [26] Have excessive insulin resistance defined as having received a total daily dose of insulin >1.5 U/kg at the time of screening

Prior/Concomitant Therapy

- [27] Glucocorticoid therapy: Receiving chronic (lasting longer than 14 consecutive days) systemic glucocorticoid therapy (including IV, intramuscular, SC, or oral, but excluding topical, intraocular, intranasal, intra-articular and inhaled preparations) or have received such therapy within 8 weeks immediately prior to screening (Visit 1) with the exception of replacement therapy for adrenal insufficiency
- [28] Have used insulin human inhalation powder (Afrezza®) within 90 days prior to screening (Visit 1)
- [29] Are currently taking traditional medicine (herbal medicine or patent medicine) with known/specified content of anti-hyperglycemic effects within 90 days prior to screening
- [30] Have used CSII for more than 14 days within the 90 days prior to screening (Visit 1)
- [31] Receiving any oral or injectable medication intended for the treatment of diabetes mellitus other than insulins in the 90 days prior to screening (Visit 1), EXCEPT for those patients with metformin at a stable dose for more than 90 days prior to Visit 1. Metformin will be discontinued at Visit 2 in accordance with local regulation

Prior/Concurrent Clinical Trial Experience

- [32] Are currently enrolled in any other clinical trial involving an IP or any other type of medical research judged not to be scientifically or medically compatible with this study
- [33] Have participated in a clinical trial involving an IP within the last 30 days. If the previous IP has a long half-life, 3 months or 5 half-lives (whichever is longer) should have passed
- [34] Have previously completed or withdrawn from this study or any other study investigating LY900014 after receiving at least 1 dose of the IP

Other Exclusions

- [35] Are investigator site personnel directly affiliated with this study and/or their immediate families. Immediate family is defined as a spouse, parent, child, or sibling, whether biological or legally adopted
- [36] Are Lilly employees (including employees, temporary contract workers, or designees responsible for the conduct of the study)
- [37] Are unable and/or unwilling to provide informed consent, to make themselves available for the duration of the study, or to abide by study procedures

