- Must remain abstinent or use 1 highly effective method of contraception or a combination of 2 effective methods of contraception for the entirety of the study (Appendix 7)
- Test negative for pregnancy at the time of screening (Visit 1). Note: a local urine or serum pregnancy test is conducted at Visit 8.
- [8] Have access to a telephone or alternative means for close monitoring and communications
- [9] Have refrigeration in the home or have ready access to refrigeration for storage of insulin therapy
- [10] Is a patient who the investigator has determined can be randomized and maintain the treatment regimens based on their previous medical history, including insulin dosing regimens, hypoglycemic episodes, and glycemic control
- [11] Capable of, willing, and desirous to do the following:
 - Inject insulin with the use of an insulin injection device (insulin pen) according to included directions
 - Perform self-BG monitoring, including 10-point SMBG on designated days (patients using a personal continuous glucose monitoring [CGM] or flash glucose monitoring [FGM] device for insulin dosing decisions must still use the study glucose meter according to the protocol)
 - o Participate in two 4-hour mixed-meal tolerance tests (MMTTs) and consume a standardized meal for the tests
 - Follow an algorithm for basal insulin adjustment and individualized prandial insulin dosing using fixed pattern adjustment or carbohydrate counting as agreed upon with the investigator
 - Comply with the use of the study insulin and scheduled visits
 - Complete the patient diary and questionnaires
- [12] Considered healthy (apart from T1D) upon completion of medical history, physical examination, vital signs, electrocardiogram (ECG), and analysis of laboratory safety variables, as judged by the investigator

Informed Consent

[13] Have given written informed consent to participate in this study in accordance with local regulations.

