7.2. Method of Treatment Assignment

Patients who meet all criteria for enrollment will be randomized to double-blind treatment at Visit 8. Assignment to treatment groups will be determined by a computer-generated random sequence using an interactive web-response system (IWRS). Patients will be randomized to 1 of the 2 treatment groups in a 1:1 ratio. Stratification will be by country (China vs. Other), HbA1c stratum (≤8.5% vs. >8.5% at Visit 7), type of basal insulin during the lead-in period (glargine U-100 vs. degludec U-100), and use of metformin at study entry (yes vs. no).

The IWRS will be used to assign all IP during the study, including insulin lispro during the lead-in period. The IWRS will be used to assign prefilled pens containing double-blind IP to each patient randomized to the 2 blinded treatment groups. Site personnel will confirm that they have located the correct prefilled pens by entering a confirmation number found on the prefilled pens into the IWRS.

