7.7. Concomitant Therapy

Guidance on restrictions for concomitant therapies is provided in Table ITSD.8.

Table ITSD.8. Concomitant Medications

Drug Class	Acute Use	Chronic Use	Safety Follow-Up Period	Conditions for Use
NPH, insulin glargine U-300, insulin detemir, insulin degludec U-200	No	No	Yes	
Regular human insulin	No	No	Yes	May be used in emergencies for up to 14 consecutive days
Premixed insulin or premixed insulin analog	No	No	Yes ^a	May be used in emergencies for up to 14 consecutive days
Affreza® (inhaled insulin), or premixed human or premixed analog insulin	No	No	No	May be used in emergencies for up to 14 consecutive days
Any noninsulin diabetes treatment therapy	No	No	No	
Systemic glucocorticosteroid (including IV, intramuscular, SC, or oral preparations, but excluding topical, inhaled, intraocular, intra-articular, or intranasal preparations)	Yes	No	No	During the lead-in period, allow 1-time use for ≤14 consecutive days. During all other study periods, allow use for a total of ≤21 days.

Abbreviations: IV = intravenous; NPH = neutral protamine Hagedorn; SC = subcutaneous.

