8.1.1. Permanent Discontinuation from Study Treatment

Patients will be discontinued from the IP in the following circumstances:

- The investigator may decide that the patient should stop IP. If this decision is made because of an AE, SAE, or a clinically significant laboratory value, the study drug is discontinued for that patient and appropriate measures are to be taken. Lilly or its designee is to be alerted.
- The patient requests to discontinue IP.
- If the patient becomes pregnant.
- If an investigator, study site personnel performing assessments, or patient is unblinded, the patient must discontinue IP.
- If the patient, for any reason, requires treatment with another therapeutic regimen or therapeutic agent that has been demonstrated to be effective for treatment of the study indication. Discontinuation from IP should occur prior to introduction of the new agent.
- Use of prohibited concomitant medication (see Table ITSD.8).
- If the patient has not taken IP for more than 14 consecutive days.
- **Discontinuation due to a hepatic event or liver test abnormality.** Patients who are discontinued from investigational product due to a hepatic event or liver test abnormality should have additional hepatic safety data collected via CRF.

Discontinuation of the investigational product for abnormal liver tests **should be** considered by the investigator when a patient meets one of the following conditions after consultation with the Lilly designated medical monitor:

- alanine aminotransferase (ALT) or aspartate aminotransferase (AST) >8X upper limit of normal (ULN)
- ALT or AST >5X ULN for more than 2 weeks
- ALT or AST >3X ULN and total bilirubin level (TBL) >2X ULN or international normalized ratio (INR) >1.5
- ALT or AST >3X ULN with the appearance of fatigue, nausea, vomiting, right upper-quadrant pain or tenderness, fever, rash, and/or eosinophilia (>5%)
- alkaline phosphatase (ALP) >3X ULN
- ALP >2.5X ULN and TBL >2X ULN
- ALP >2.5X ULN with the appearance of fatigue, nausea, vomiting, right quadrant pain or tenderness, fever, rash, and/or eosinophilia (>5%)

Patients discontinuing from the investigational product prematurely for any reason should complete adverse event and other follow-up procedures per Section 2 (Schedule of Activities), Section 9.2 (Adverse Events), and Section 9.4 (Safety) of this protocol.

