9.1.4.3. Mixed-Meal Tolerance Test

A 4-hour MMTT will be performed in all patients at baseline (Week 0, Visit 8) and at the end of the 26 weeks of treatment (Visit 18). For patients who remain in the study after early discontinuation of IP, MMTT assessment will NOT be performed. Patients will be instructed to fast for at least 8 hours prior to the administration of the MMTT at the study site.

The MMTT can occur 0 to 4 days prior to the visit. The MMTT can be rescheduled up to 2 times within the visit window, ideally at 24-hour intervals, if the patient does not meet the target FBG. It is preferred for the rescheduled MMTT to occur as close to the visit date as possible.

Target FBG prior to the MMTT: Patients must have an FBG in the range of 71 to 180 mg/dL (3.9 to 10.0 mmol/L) prior to starting the MMTT. If the glucose is outside of this range, the MMTT should be rescheduled.

In order to increase the likelihood of having patients arrive on the morning of the MMTT within the target FBG range, note the following:

- Patients should be instructed to avoid major changes in dietary intake or physical activity during the 3 days prior to the MMTT.
- Patients should be instructed to inject basal insulin according to their usual schedule, but should not administer correction doses with their rapid-acting insulin within 4 hours of the start of the MMTT.

During the 8-hour fasting period and up to 2 hours prior to the start of the MMTT, episodes of non-severe hypoglycemia (symptoms or BG \leq 70 mg/dL [3.9 mmol/L]) can be treated with 15 to 20 grams of carbohydrate. If an episode requires more than approximately 20 grams of carbohydrate within 8 hours of the start of the MMTT or the patient experiences a severe episode requiring assistance, the patient should be instructed to notify the site and the MMTT must be rescheduled.

Test Meal: The MMTT meal will consist of a standardized liquid nutrition shake(s) (approximately total energy 700 kcal and 100 grams of carbohydrates, such as Ensure Plus®, Abbott Nutrition), Patients are expected to consume the meal within 15 minutes. Patients should consume the same test meal for both the baseline and end of primary treatment period MMTT, if possible.

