The definitions of baseline and postbaseline for the efficacy and safety analyses depend on which analysis period is being used. The following analysis periods will be used:

- Lead-in Period Visits 2-8
- 26-Week Treatment Period from randomization to Week 26 prior to discontinuation of IP
- 26-Week Treatment Period and Safety Follow-Up Visit from randomization to Visit 801 (including all data regardless of IP use)

The data on IP is defined based on the following rules:

- for data only measured at an office visit
  - MMTT postbaseline data will be considered as data on IP if the MMTT performance date is on or prior to the last IP dose date
  - Other postbaseline data (for example, vital signs, laboratory tests, and questionnaires) will be considered as data on IP if the measurement date is on or prior to the cutoff date defined as 14 days after the last IP dose date
- for data collected as running records with an exact date stamp such as adverse events (AEs) and diary entries where the dates of the measures were not tied with the date of an office visit, postbaseline data with dates ≤ (last study drug dose date +1) will be considered as data on IP.

Table 6.2 describes the rules for determining the patient population, baseline and postbaseline observations for the different analysis periods.

For continuous measures, summary statistics will include sample size, mean, SD, median, minimum, and maximum for both the actual and the change from baseline measurements. Least-squares (LS) means and standard errors derived from the analysis models will also be displayed. Treatment comparisons will be displayed showing the treatment difference LS means and the 95% CIs for the treatment differences, along with the p-values for the treatment comparisons.

For categorical measures, summary statistics will include sample size, frequency, and percentages. Fisher's exact test will be used for treatment comparisons.

For laboratory values, Systeme International (SI) units will be presented. Therefore, both % and mmol/mol will be presented for HbA1c and mmol/L will be presented for glucose measurements.

All baseline measures will be analyzed using an analysis of variance (ANOVA) model that has treatment as the model terms.

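### Table ITSD.8 omits the adrenal-insufficiency exception granted by exclusion [27], so a patient admitted on replacement therapy has no compliant way to continue it on study drug (minor)

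*Protocol*

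**What the plan says.** **Entry.** Protocol section 6.2, criterion [27], excludes patients on systemic glucocorticoids for more than 14 consecutive days, whether current or within 8 weeks before screening, "with the exception of replacement therapy for adrenal insufficiency". Topical, intraocular, intranasal, intra-articular and inhaled preparations are also outside the criterion.

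**On study.** The systemic glucocorticosteroid row of Table ITSD.8 (section 7.7) covers injected and oral preparations and leaves out the same five routes. It marks acute use as allowed, and chronic use and use in safety follow-up as not allowed. The lead-in limit is a single course of at most 14 consecutive days. For the rest of the study the row reads "During all other study periods, allow use for a total of ≤21 days". Adrenal replacement is not mentioned, and the table's only footnote concerns premixed insulin.

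**Consequence.** Section 8.1.1 lists circumstances in which patients are to be taken off IP, in mandatory wording. One is "Use of prohibited concomitant medication (see Table ITSD.8".

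**What happens to the data.** For patients who stay in the study off IP, section 9.1.4.3 says: "For patients who remain in the study after early discontinuation of IP, MMTT assessment will NOT be performed". The primary HbA1c analysis uses on-IP data only. For laboratory tests, SAP section 6.1 closes the on-IP period at "the cutoff date defined as 14 days after the last IP dose date".

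**The concern.** The entry criterion and the concomitant-medication table treat the same patient in opposite ways. The table repeats every route exemption in [27] but drops the one exemption that concerns an indication. Nothing else in the protocol or SAP restores it.

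The exception appears to have been meant to last beyond entry. Where the protocol admits a patient on a drug but wants that drug stopped, it says so. For metformin, [31] states: "Metformin will be discontinued at Visit 2 in accordance with local regulation". Criterion [27] contains no such instruction. This is an inference from silence, but it favours continued replacement as the intent.

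An investigator with such a patient has three options: stop IP and lose the patient's Week 26 data from the on-IP analyses, depart from 8.1.1 by continuing both, or withdraw a replacement therapy that the entry criterion accepts. None is satisfactory. The matter is mainly one of patient safety and protocol coherence, and only marginally one of power.

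**Working it through.** **1. Can daily replacement fit the acute allowance?** Period lengths come from protocol section 5.1 and limits from Table ITSD.8.

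| Period | Days of daily use | Limit | Limit passed on |
|---|---|---|---|
| Lead-in | 8 × 7 = 56 | 14 consecutive, once | day 15 |
| Treatment | 26 × 7 = 182 | 21 in total | day 22 |
| Treatment plus follow-up | 30 × 7 = 210 | 21 in total | day 22 |

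It cannot fit.

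**2. When does IP stop, and which HbA1c values survive?** Post-baseline HbA1c is scheduled at Weeks 4, 8, 12 and 26, each ±7 days (protocol section 2). Week 4 therefore falls on days 21 to 35 and Week 8 on days 49 to 63. The on-IP window ends at last dose + 14 days. The text allows three readings.

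- *Lead-in lispro counts as IP.* Section 7.2 supports this: "The IWRS will be used to assign all IP during the study, including insulin lispro during the lead-in period". The stop falls on lead-in day 15. The patient is not randomized and no primary data are lost.
- *IP is only the randomized product, and the use already counts as chronic.* The stop comes at about day 1 and the window closes at 1 + 14 = day 15, before the earliest Week 4 date (day 21). No post-baseline HbA1c qualifies, so the patient drops out of the primary model, which needs at least one.
- *IP is only the randomized product, and the 21-day total governs.* The stop comes by day 22 and the window closes at 22 + 14 = day 36. Week 4 (latest day 35) counts; Week 8 (earliest day 49) does not.

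Under the second and third readings the Week 26 HbA1c is excluded from the on-IP analyses and the Week 26 meal test is not performed.

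**3. The plan's own power figure.** Inputs from protocol section 10.1: margin 0.4, SD 1.1, true difference 0, 149 completers per arm, 2-sided 95% CI.

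Power = Φ(0.4 / (1.1 × √(2/n)) − 1.96)

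For n = 149: 0.4 / (1.1 × 0.11586) = 3.139; 3.139 − 1.960 = 1.179; Φ = 88.1%. The noncentral t with 296 degrees of freedom gives 87.9%. Both agree with the stated 87% to within about a point. For enrolment, 298 / 0.85 = 350.6, against about 350 stated.

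**4. Effect on power.** The documents give no prevalence of adrenal insufficiency, so a range of 0% to 1% is assumed here.

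| Assumed prevalence | Patients of 350 |
|---|---|
| 0% | 0 |
| 0.2% | 0.7 |
| 0.5% | 1.75 |
| 1% | 3.5 |

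| Completers per arm | Power, normal | Power, t |
|---|---|---|
| 149 | 88.1% | 87.9% |
| 148 | 87.9% | 87.7% |
| 147 | 87.7% | 87.4% |

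The plan's dropout allowance is 350 − 298 = 52 patients, which would absorb a loss of 4.

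**The case against.** The best counter-argument is that such a patient may never be admitted. Escaping [27] is not enough; every criterion must be met. Inclusion [12] asks that the patient be "Considered healthy (apart from T1D) upon completion of medical history" and other assessments, as judged by the investigator. Exclusion [14] bars any other condition that prevents completion of the protocol, and [37] bars those unable to follow its procedures. If Table ITSD.8 is absolute, [14] arguably excludes these patients. The exception in [27] could also be read as qualifying only past use within the 8 weeks before screening. These points reduce the number affected, perhaps to zero. They do not remove the conflict, because each leaves the written exception with little or no effect.

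The mandatory stop can also be questioned. Section 7.7 introduces the table as guidance, and glucocorticoids are limited rather than banned outright. But chronic use is marked as not allowed, and 8.1.1 makes the table the trigger in mandatory terms.

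The reading that counts lead-in lispro as IP is the weakest of the three. Protocol section 2 (pregnancy-test footnote) and SAP Table 6.2 both place the start of IP at randomization. The conflict does not depend on that reading.

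The point about size stands in full: the prevalence is assumed, and any expected loss is within the dropout allowance.

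**Conclusion.** The plan is wrong as written on this point, and the error is minor. Followed literally, Table ITSD.8 and section 8.1.1 would take an eligible patient off IP, or off replacement therapy, for a reason known and accepted at screening. This rests on the natural reading of [27], in which the exception covers current as well as past use, and on taking the chronic-use entry in the table at face value.

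Few patients are involved, possibly none: 0 to about 4 of 350 on an assumed prevalence of 0% to 1%. At the upper end, power falls by about 0.4 percentage points and stays above the stated 87%. The cause predates randomization and is unrelated to the assigned arm, so no directional bias is expected and the noninferiority conclusion would not materially change.

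**What to change.** In the systemic glucocorticosteroid row of Table ITSD.8, state that glucocorticoid replacement for adrenal insufficiency is permitted in all study periods and does not count towards the 14-day or 21-day limits. Section 8.1.1 is then not triggered and needs no edit of its own. This matches the apparent intent of [27].

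If the sponsor does not want these patients in the trial, delete the exception from [27] instead. At most a handful of candidates would become ineligible.

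Either change is one clause in the next amendment or a clarification letter. Neither adds procedures or visits, or requires a larger sample.
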